7.2.1.1.2 Estimation of LMP and Date of Conception

The International Classification of Diseases, 10th Revision, Clinical Modification (ICD-10-CM) coding system includes several codes (Z3A**) that describe the estimated gestational age of the fetus. For example, the ICD-10-CM code Z3A.12 represents 12 weeks of gestation and Z3A.23 represents 23 weeks of gestation. The date of the LMP is estimated by subtracting the number of weeks of gestation associated with the Z3A code from the corresponding date of service of that

claim. Validation of LMP date estimated using Z3A codes has indicated good performance, with a median difference of 4.0 days (interquartile range: 2.0 – 10.0) between LMP date based on Z3A codes and adjudicated (via medical record review) LMP date (Chomistek et al., 2023b). The LMP date corresponds to a gestational age of 0 weeks. Operationally, the start of pregnancy (the date of conception) is defined as gestational age equal to 2 weeks, 0 days.

Most pregnancies in the ORD include Z3A codes that permit LMP estimation for a pregnancy even before the pregnancy outcome is observed. However, there is a small fraction of pregnancies that do not include these Z3A codes; in these cases, Optum employs outcomes-based algorithms that estimate the LMP by counting back the number of weeks from the occurrence of the outcome, with different outcomes assigned different weeks of gestation (Hornbrook et al., 2007).

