7.2.1.1.1 Pregnancy Identification

To identify pregnancies, Optum searches the administrative claims for combinations of diagnostic and procedure codes indicating a pregnancy, delivery, or pregnancy endpoint, as well as prenatal care. This process has been described previously by Bertoia et al. (2022). Women are required to have at least one pregnancy-related health insurance claim to be considered as having a pregnancy. The first pregnancy-related claim is identified a median of 74 days (range 1, 294; mean 114.3 [standard deviation 80.1]) after last menstrual period (LMP). If a woman has more than one eligible pregnancy during the study period, each of the qualifying pregnancies may be included. Analyses will account for the correlations between multiple pregnancies for a given woman. It should be noted that the first observed pregnancy per woman in the claims database might not be that woman's first pregnancy.

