Cohort entry will be set at the date of dispensing in the Nemolizumab Cohort (i.e., the earliest nemolizumab administration date during a pregnancy) and the Other AD/PN Treatment Cohort,

and the corresponding day of gestation among unexposed pregnancies, rounded down to the nearest week. For example, for pregnancies entering the Week 8 Cohort, we will first select all pregnancies with no nemolizumab or other AD/PN treatment from 5 times the half-life before ECD through 7 weeks' + 6 days' gestation. Then, we will assign the pregnancies that receive nemolizumab during Week 8 (8 weeks + 0 days through 8 weeks + 6 days) to the nemolizumab-exposed group, those that received another AD/PN treatment to the other treatment-exposed group, and those that did not receive nemolizumab or another AD/PN treatment during Week 8 to the unexposed group. Cohort entry among the Week 8 nemolizumab and comparator cohorts will be set to 8 weeks' + 0 days. The pregnancies in the Week 8 exposed cohort will no longer be eligible for inclusion in subsequent weekly cohorts. However, the pregnancies in the Week 8 unexposed group will go on to be eligible for inclusion in the Week 9 Cohort, at which point their exposure status would be reassessed during Week 9 (9 weeks + 0 days through 9 weeks + 6 days). A pictorial depiction of this process can be found in Figure 1 and key pregnancy dates can be found in Table 1. If the study size does not permit weekly sequential cohorts, the cohorts may be collapsed into longer (e.g., 2-week, 4-week) intervals as needed.

Figure 1 Sequential cohort design, depicting an example of cohort entry for the Week 7 and Week 8 cohorts

Abbreviations: AD, atopic dermatitis; ECD, estimated conception date; PN, prurigo nodularis

Table 1 Pregnancy dates

Date	Definition
LMP	First day of last menstrual period 0 gestational weeks ^{0/7 days}
Gestational age	Weeks of gestation Anchored by LMP Number of completed weeks elapsed after LMP

Date	Definition
ECD	Estimated as LMP + 14 days 2 gestational weeks ^{0/7 days}
First trimester	Begins at ECD minus 5 times the half-life of the treatment Ends at LMP + 97 days
Second trimester	Begins at LMP + 98 days Ends at LMP + 195 days
Third trimester	Begins at LMP + 196 days Ends at pregnancy outcome
Pregnancy period	Begins at ECD minus 5 times the half-life of the treatment Ends at pregnancy outcome

Abbreviations: ECD, estimated conception date; LMP, first day of last menstrual period

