MCMs will be identified in live born infants, and study drug exposure will be assessed in the first trimester. However, the exact timing of the development of malformations is typically unknown. Additionally, while the use of ICD-10-CM Z3A codes to estimate LMP has been shown to be accurate ([Chomistek et al., 2023b](#)), not all pregnancies have Z3A codes, and some degree of measurement error is expected in estimating the beginning of pregnancy. The resulting exposure misclassification due to estimated LMP is not expected to be differential with respect to exposure. A sensitivity analysis will explore alternative exposure windows that are more conservative.

It is possible that selection bias may arise due to differential loss to follow-up (i.e., if pregnant women who receive nemolizumab are more or less likely to be lost to follow-up than those who are exposed to other AD/PN treatments or who are unexposed), though we expect censoring to be non-differential with respect to exposure and outcome status. To check this assumption, we will compare the baseline characteristics of pregnancies with an observed outcome versus those who were censored before the end of pregnancy. We will also describe the frequency of censoring events according to nemolizumab exposure status.

Residual confounding is always a concern in observational studies. While propensity score models can account for a large number of measured pre-specified and empirically derived variables, some variables may have a greater degree of misclassification, and some confounders may not be measured. For example, due to ICD-10 coding limitations, claims data tend to have incomplete capture of smoking status. However, the degree of residual confounding due to unmeasured factors may be reduced if proxies of unmeasured factors are included in the models ([Guertin et al., 2016](#)). A quantitative bias analysis will assess the impact of residual confounding on the observed results.

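### Pregnancies without a Z3A code are dated from their own outcome, so their exposure window and entry week depend on the outcome analysed; Section 7.10 considers this error only by exposure, and no planned sensitivity analysis tests it.

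*Protocol*

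**What the plan says.** Section 7.2.1.1.2 gives two dating rules. Where a Z3A code exists, LMP is "estimated by subtracting the number of weeks of gestation associated with the Z3A code" from the date of service. This can be done before the outcome is known. The section then says that "there is a small fraction of pregnancies that do not include these Z3A codes". For those, LMP is found by counting back from the outcome, "with different outcomes assigned different weeks of gestation". The protocol does not state the weeks assigned to each outcome, the size of the fraction, or its split by outcome.

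LMP then drives the design:

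- Table 1 sets the estimated conception date (ECD) at LMP plus 14 days.
- Section 7.3.6.1 starts the nemolizumab window 95 days before ECD and forms cohorts by gestational week.
- Section 7.7.3 matches on gestational week.
- Table 2 censors the spontaneous abortion and termination analyses at 20 weeks.

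Section 7.10 concedes that some pregnancies lack Z3A codes and that LMP carries error. It continues: "The resulting exposure misclassification due to estimated LMP is not expected to be differential with respect to exposure". It then points to alternative exposure windows as the check.

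**The concern.** A design that emulates a target trial needs time zero and exposure status to be fixed without reference to what happens later. The Z3A rule allows this; the fallback rule does not. A loss without a Z3A code has a gestational age at the event that is a constant chosen by outcome type, not a measurement, and its exposure look-back moves with that constant.

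If the assigned week is later than the true week, LMP and ECD are placed too early. The look-back then reaches further into the past, and the loss is more often classed as exposed. If the assigned week is too early, the reverse happens. Either way exposure is misclassified differently in losses and in Z3A-dated continuing pregnancies. The statement in Section 7.10 does not cover this, because non-differentiality with respect to exposure says nothing about dependence on outcome. A larger sample does not remove the bias.

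**Working it through.** **Reproducing the protocol's dates.** 5 × 18.9 = 94.5 days, rounded up to 95 (Appendix D). ECD is LMP + 14 days, or 2w0d. Both agree with the text.

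**Size of the dating error.** Let D be the outcome date, G the true gestational age at loss in days, and w the assigned week.

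- Assigned LMP = D − 7w; true LMP = D − G; error = G − 7w days (positive means too late).
- The 95-day look-back then really starts 95 + 7w − G days before the true ECD.
- For a loss at 9 weeks (G = 63): w = 12 gives 95 + 84 − 63 = 116 days; w = 8 gives 95 + 56 − 63 = 88 days.
- With w = 10 and true losses at 5 to 19 weeks, LMP lies between 5 weeks too early and 9 weeks too late.

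**Do the planned analyses test this?** Section 7.7.3.5.4 has four runs. Three move the start of the window for every pregnancy, to 57 days, 29 days or ECD itself (shifts of 38, 66 and 95 days). The fourth requires two or more dispensings. In all four, ECD for a loss without a Z3A code is still D − 7w + 14. None varies w or restricts to Z3A-dated pregnancies.

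**Effect on a null comparison.** All inputs are assumptions except the 95 days and the 14% loss risk (Table 3). Loss occurs at a mean of 9 weeks. Treatment stops uniformly between 365 days before and 30 days after ECD (395 days). Fills are f = 28 or 56 days apart, so the last fill falls f/2 before stopping on average. A share s of losses is outcome-dated.

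- True probability of exposure: p = (30 + 95 − f/2)/395. For f = 28, p = 111/395 = 0.281.
- Change in that probability among losses: δ = s × 7 × (w − 9)/395.
- Apparent risk if exposed: 0.14(p + δ)/[0.14(p + δ) + 0.86p].
- Apparent risk if unexposed: 0.14(1 − p − δ)/[0.14(1 − p − δ) + 0.86(1 − p)].

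Example with s = 0.30, w = 12, f = 28:

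- δ = 6.3/395 = 0.0159
- exposed risk = 0.04157/0.28324 = 0.1468
- unexposed risk = 0.09843/0.71676 = 0.1373
- ratio = 1.07, where the truth is 1.00

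A simulation with the same inputs (standard deviation of gestational age at loss assumed to be 2.5 weeks) gives these ranges over w = 8 to 12 and both fill intervals:

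| Share of losses outcome-dated | Null exposed/unexposed ratio |
|---|---|
| 10% | 0.99–1.02 |
| 30% | 0.97–1.07 |
| 60% | 0.95–1.15 |

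With w = 9, equal to the assumed mean, the ratio is 1.00. The sign depends on a constant the protocol does not state. The same simulation for nemolizumab against a comparator with a 70- to 123-day look-back (Appendix D) stays within about 2% of 1 at a 30% share and 3% at 60%. The calculation ignores matching and weighting, so it shows order of magnitude only.

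**How large might the share be?** Suppose 5% of all pregnancies lack a Z3A code. Spread evenly, 5% of losses are outcome-dated. If all were spontaneous abortions, the share is 5/14 = 36% of those events. A fraction that is small overall does not settle the question.

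**The case against.** The strongest reply is that the protocol calls the fraction small and discloses LMP error, and that with 5–10% of losses outcome-dated the ratio is only 0.99–1.02, in outcomes sized for relative risks of 2 to 3. The active-comparator contrast is nearly untouched. The primary outcome, major congenital malformations, is assessed in live births, so the early-loss argument does not reach it. All of this stands and limits the weight of the point. It does not answer the mismatch in Section 7.10 or the absence of any run on the LMP source.

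Two stronger readings are tempting.

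- **Missing Z3A codes are concentrated in early losses.** A reader might infer this from Section 7.2.1.1.1: "The first pregnancy-related claim is identified a median of 74 days" after LMP, which is 10w4d. That median covers all identified pregnancies and says nothing about Z3A coding, and a claim for a loss can itself carry a Z3A code. Concentration is plausible, but the documents do not state it.
- **Z3A dating is itself at fault.** Table 1 defines gestational age as "Number of completed weeks elapsed after LMP", so subtracting whole weeks puts LMP 0–6 days late. This applies to every Z3A-dated pregnancy, whatever its arm or outcome, so it does not separate losses from continuing pregnancies. A constant 3-day correction would leave alignment between arms essentially unchanged (mean gestational-age gap 3.24 against 3.23 days). The validation result (median difference 4.0 days, interquartile range 2.0–10.0, direction not stated) gives no basis for such a shift.

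**Conclusion.** The point holds in a limited form. For pregnancies without a Z3A code, the outcome under analysis sets exposure status, entry week and the gestational clock. Section 7.10 argues about a different kind of error, and the check it relies on cannot reveal this one. The exposed analyses are mainly the early-loss outcomes against the Unexposed Cohort.

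The likely bias is small if few losses are affected (1–2% at a 10% share) and could reach about 15% at a 60% share with an assigned week three weeks above the mean. These figures rest on the assumed timing of losses, fills and stopping, and on an assumed share. The documents fix neither the size nor the direction. This is a worthwhile, inexpensive improvement to secondary analyses, not a threat to the primary result.

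**What to change.** 1. In Section 7.7.3.5, add a sensitivity analysis for spontaneous abortion, elective termination and ectopic pregnancy. Shift the assigned gestational week of outcome-dated pregnancies earlier and later, for example by 2 and 4 weeks, and reassign ECD, exposure and entry week each time. Add a second run restricted to Z3A-dated pregnancies.
2. Report the share of pregnancies dated from the outcome, by outcome and by cohort.
3. Correct Section 7.10 to say that this dating error depends on the outcome and that the alternative exposure windows do not test it.

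The cost is some programming, with re-matching in each data source for each run. The Z3A-only run is itself a selected subset, so it should be read together with the shifted runs. The main analysis need not change. In particular, imputing gestational age from Z3A-dated losses would still date by outcome, and it would leave most of the bias (about 1.05 at a 30% share) if undated losses occur earlier.

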7.2.1.1.3 Infant Linkage

The identification of infant outcomes, such as MCMs or SGA birth, relies on data from the infant's claims record rather than the mother's claims record. Mother and infant records will be linked through the presence of a common unique family insurance identifier. This number is used by health plans to identify all members of a family who are covered by the same insurance plan for the purposes of defining coverage, payment, and reimbursement, providing assurance that mother-infant pairs identified in this manner are accurate. In addition, claim(s) relating to the delivery must be within 7 days of the infant's birth date (or 32 days for multiples). This linkage has been used to address regulatory questions by pharmaceutical companies about the effects of drugs on pregnancy (Carman et al., 2007; Wyszynski et al., 2016).

The fraction of identified deliveries that cannot be matched to an infant is likely due to the infant being covered under a different health insurance from the mother. This may occur if the newborn were to be added to the other parent's plan (rather than the mother's), if the parents were to switch from individual plans to family health plans, or if the mother were covered under her parents' policy (in which case a separate plan would need to be purchased for the infant).

7.2.2 Optum's Market Clarity Data

Beginning with the 2029 PSUR, patients will also be identified within Optum's Market Clarity Data. This database integrates medical and pharmacy claims data with clinical data for approximately 80-85% of patients in Optum's EHR Research Database from January 2007 through the present. Market Clarity includes data on over 82 million patients as of March 2024, with over 68 million of those having eligibility information available.

Optum's EHR Research Database is a patient-level database that integrates multiple electronic medical record data systems with medical billing, prescription, and practice management data. The database incorporates relevant clinical data, as recorded during routine clinical practice, for patients in both ambulatory and inpatient settings. Data include medical records, laboratory results, and drug prescription (including number of refills) and administration data.

The database also includes data derived from free-text clinical notes relating to the medical encounters. Optum uses a generalized natural language processing (NLP) system developed to extract and organize concepts from free text into semi-structured fields. The database contains pertinent attributes, sentiments, and modifiers to the concepts. Re-examination of the source text

corresponding to the NLP-extracted observations is possible with appropriate permissions.

In Market Clarity, Optum's EHR data are supplemented with medical and pharmacy claims from the ORD and from third-party data sources. The availability of linked pharmacy claims data in Market Clarity provides the opportunity to augment the data on drug prescriptions available in the EHR, which enables more comprehensive identification of all drugs received by patients through pharmacy drug dispensings. This linkage will accordingly improve the ability to capture nemolizumab initiation and subsequent drug dispensings within the database.

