7.7.1 Annual Monitoring

Optum will tabulate counts of pregnancies exposed to nemolizumab (from 95 days [i.e., 5 times the half-life], or approximately 14 weeks, before ECD through the end of pregnancy) as well as counts of live births from these pregnancies, and the results will be included in the PSURs. Women with nemolizumab-exposed pregnancy episodes will be described according to baseline demographic and clinical characteristics (a subset of those mentioned in [Section 7.4.3](#)). Additionally, the overall number of eligible pregnancies will be tabulated and described according to the same baseline demographic and clinical characteristics. All analyses will be descriptive, including the number of observations, mean, standard deviation, median, interquartile range, and range for all continuous variables and counts and percentages for each binary or categorical variable. Counts from Optum's Market Clarity Data will be added starting with the 2029 PSUR, and additional data partners will be added based on the results of the feasibility assessment to ensure sample size projections are met (as described in [Section 7.7.2](#)).

Outcome counts (except for live births), matching, propensity score estimation, meta-analyses, and sensitivity analyses will not be performed until the final report.

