7.7.3 Final Analysis

For the final study report, Optum will match nemolizumab-exposed pregnancies to the two comparator groups (Other AD/PN Treatment Cohort and Unexposed Cohort) in a 1:4 ratio based on maternal age at cohort entry, gestational week of dispensing, indication, and calendar week, separately within each data source. If the study size does not permit matching in these categories (or intervals), the sequential cohorts may be collapsed to 2-week intervals for gestational week at cohort entry or wider categories for maternal age at cohort entry and calendar time. A variable matching ratio of 1:up to 4 may also be considered.

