7.7.3.3 Comparative Analyses

Nemolizumab-exposed pregnancies will be matched to pregnancies in the two comparator groups in a 1:4 ratio based on maternal age at cohort entry, gestational week of dispensing, indication, and calendar week, separately within each data source. For all pregnancy and infant outcomes assessed at the end of pregnancy or during pregnancy, we will estimate RRs comparing the Nemolizumab Cohort to the comparator cohorts using robust Poisson regression models (for MCMs and SGA births) and HRs using Cox proportional hazards models (for all other outcomes). All comparative analyses will be performed incorporating stabilized IPTW to adjust for potential confounding. All analyses will be conducted by data source and then meta-analyzed (as described in [Section 7.7.3.4](#)).

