7.7.3.4 Meta-analysis

For the final report, all of the comparative analyses outlined in [Section 7.7.3.3](#) will be conducted as meta-analyses. No individual-level data will be pooled across data sources. Standard software for combining estimates across data sources (e.g., [Comprehensive Meta-Analysis or a similar package](#)) will be utilized. This software package performs the meta-analyses and generates diagnostics for assessing heterogeneity along with tabular and graphical output (forest plot for display of results).

Database-specific estimates (HRs and CIs or exposure-specific events and person-time) will be analyzed using the software package and a summary of the data (tabular and forest plots) along with pooled estimates and CIs as well as diagnostic measures of heterogeneity will be provided. Results from both random effects and fixed effects meta-analysis will be reported. Additional details of the planned meta-analyses will be included in the SAP.

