7.8.2 Optum

Optum is responsible for site-specific analyses (annual counts, feasibility report, final report) as well as combining results from all research partner sites (annual counts starting in 2030 and final report). The conduct and reporting of this study follows Optum Epidemiology's SOPs that are consistent with the International Society for Pharmacoepidemiology (ISPE)'s Guidelines for Good Pharmacoepidemiology Practices (GPP) (ISPE, 2015) as well as The European Network of Centres for Pharmacoepidemiology and Pharmacovigilance (ENCePP): Guide on Methodological Standards in Pharmacoepidemiology and the EMA Guideline on Good Pharmacovigilance Practices: Module VIII – Post-authorization Safety Studies. For pregnancy safety studies such as this, the suggested study design and methodology are consistent with the FDA draft guidance document Postapproval Pregnancy Safety Studies Guidance for Industry (<https://www.fda.gov/regulatory-information/search-fda-guidance-documents/postapproval-pregnancy-safety-studies-guidance-industry>). In particular, the SOPs in place at Optum prescribe that processes and deliverables are documented, reviewed, and validated in sufficient detail to allow for subsequent re-examination or replication.

The validation of analytic work typically involves a combination of a review of program logs and lists, independent coding, a review of program processes and documentation to ensure Optum SOPs are followed, and reconciliation of program code with the study protocol to ensure populations and results are consistent with what is needed for the study. Individual programs are documented and revised as needed until sign-off by a validation analyst using the validation/programming log.

The validity of the ORD for epidemiologic research (as compared with data abstracted from medical records) has been established (Dore et al., 2011; Eng et al., 2012; Loughlin et al., 2010).

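### Market Clarity contains ORD claims and the protocol has no rule against counting or pooling the same pregnancy twice; each pregnancy should be assigned to one source before matching

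*Protocol*

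**What the plan says.** Section 7.2.2 states that, from the 2029 PSUR, "patients will also be identified within" Market Clarity, in addition to the ORD. The same section says that Market Clarity's "EHR data are supplemented with medical and pharmacy claims from the ORD and from third-party data sources". Part of its claims content is therefore ORD content.

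Section 7.3.2 sets eligibility by type of source. Claims sources need six months of medical and pharmacy enrolment up to cohort entry. Linked claims-EHR sources need pharmacy coverage over the pregnancy period and an outpatient visit at least six months before cohort entry. Neither rule excludes members of the other source.

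On counts, Section 7.7.1 says that those from "Market Clarity Data will be added starting with the 2029 PSUR", and Section 7.5 uses the PSURs to judge whether the target size can be met. Section 7.8.2 makes Optum responsible for "combining results from all research partner sites (annual counts starting in 2030 and final report").

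On analysis, Section 7.7.3 has matching done "separately within each data source". Section 7.7.3.3 adds: "All analyses will be conducted by data source and then meta-analyzed". Section 7.7.3.4 states: "No individual-level data will be pooled across data sources", and "Results from both random effects and fixed effects meta-analysis will be reported".

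The only within-person correlation that the protocol addresses is repeat pregnancies of one woman (Section 7.2.1.1.1). The limitations in Section 7.10 do not mention overlap between sources.

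**The concern.** A woman with ORD claims whose provider contributes to the EHR database can be present in both sources. If her pregnancy meets both sets of criteria, it enters two matched cohorts and two effect estimates. Inverse-variance pooling then treats those estimates as coming from separate people.

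Three things are at stake:

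- **Precision.** The pooled interval is narrower than the information supports. In a safety study this can produce a false signal or overstate reassurance.
- **Heterogeneity.** Sources that share pregnancies agree partly because they share them, so the diagnostics promised in Section 7.7.3.4 look better than they should.
- **Accrual.** The target of 352 exposed pregnancies is a number of distinct pregnancies. A sum over overlapping sources overstates progress towards it.

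Since individual-level pooling is ruled out, duplicates cannot be removed at the pooling stage. This has to happen when the cohorts are formed.

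**Working it through.** **The plan's own target.** Inputs from Section 7.5 and Table 3: MCM prevalence 3%, RR 2.5 (so 7.5% against 3%), allocation 1:4, two-sided alpha 0.05, power 80%. The two-proportion formula without continuity correction gives 214 exposed linked live births, as stated. With 80% observed outcomes and 76% live births, 214 / (0.80 × 0.76) = 351.97, or 352 pregnancies. The target reproduces. It assumes 352 different pregnancies.

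**Assumption for the overlap.** The protocol gives no figure. Take two sources of equal size that share a fraction f of each source's pregnancies, exposed and comparator alike. This is an illustration only.

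**Counts.** With 352 counted over both sources, the duplicates are 352 × f/2, so the distinct number is 352 × (1 − f/2). Distinct live births are 214 × (1 − f/2), and power for RR 2.5 is recomputed at that number.

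**Pooled standard error.** Let each estimate have variance s² and let their correlation be f. The mean of the two has variance s²(1 + f)/2, while pooling under independence uses s²/2. The true standard error is therefore √(1 + f) times the reported one, and the two-sided error is 2 × [1 − Φ(1.96/√(1 + f))].

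| f | Distinct pregnancies of 352 | Power, RR 2.5 | SE factor | Two-sided error |
|---|---|---|---|---|
| 10% | 334 | 78% | 1.05 | 6.2% |
| 25% | 308 | 76% | 1.12 | 8.0% |
| 50% | 264 | 70% | 1.22 | 11.0% |

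Coverage of a nominal 95% interval is the complement: about 93.8%, 92.0% and 89.0%.

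**Heterogeneity.** The difference between the two estimates has variance 2s²(1 − f), not 2s². With no true heterogeneity, the expected Q on one degree of freedom is 1 − f instead of 1, for example 0.75 at f = 25%.

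**Weaker assumptions.**

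- *Unequal sources.* If one source is four times the other and a fraction f of the smaller is shared, the SE factor is √(1 + 2f/5). At f = 25% this is 1.05 (error 6.2%); at f = 50% it is 1.10 (error 7.4%). Of 352 counted, 352 × (1 − f/5) = 334 and 317 are distinct.
- *Only exposed pregnancies shared.* Matching is separate, so a shared exposed pregnancy need not draw the same comparators. With 1:4 matching and equal risks, the exposed group contributes 1/(1 + 1/4) = 0.8 of the variance of the log RR, so the correlation is 0.8f. The error is 7.4% at f = 25% and 9.8% at f = 50%.

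**The case against.** **The SAP may settle it.** Section 7.7.3.4 leaves further detail of the meta-analysis to the SAP, and de-duplication could be written there. This is fair as far as the pooling detail goes. But the choice of sources, their eligibility rules and the PSUR counts are set in this protocol, and the PSUR counts are reported years before the final analysis. Followed as written, the protocol allows double entry.

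**Added counts need not mean summed counts.** The wording of Section 7.7.1 could mean that Market Clarity counts are shown beside those of the ORD. Section 7.8.2 speaks of combining partner sites, and Optum holds both databases. This stands: overstated accrual is conditional on summing.

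**The size is unknown.** This also stands. The overlap and the equal source sizes are assumed, and the less favourable of these assumptions drive the larger figures. The infant linkage is described for the ORD only, so overlap among linked infants, on whom the primary MCM analysis rests, is unknown as well. Error rate is also an imperfect yardstick for a study that declares no prior hypotheses; interval coverage says the same thing in more suitable terms.

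**Stronger readings that the protocol does not support.** A reader might infer that the two sources could coincide entirely. That does not fit Section 7.2.2, since Market Clarity also draws on third-party claims and rests on EHR records. A reader might also infer that inflated counts would make the study stop adding sources too early. No count-triggered stop exists: the milestones in Section 4 are calendar dates, and Sections 7.1, 7.5 and 7.7.2 already say that more sources are needed or will be added.

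**Conclusion.** The concern holds as a flaw in the stated method. The protocol names two sources with shared content, lets the same pregnancy qualify in both, and pools their separate estimates as if independent, with no rule to prevent double entry. The direction of the effect is clear: pooled intervals too narrow, heterogeneity understated, and accrual overstated if the counts are summed.

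The size is not established. Under equal sources and equally shared comparators, the error figures of about 6%, 8% and 11% for 10%, 25% and 50% overlap are upper values for those shares; the variants computed above lie below them. The distinct counts of 334, 308 and 264 rest on equal sources and on summing. The sample-size calculation itself is correct; the fault lies in what may be counted towards it and in the independence assumed when pooling.

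**What to change.** State in Sections 7.2.2, 7.7.1 and 7.7.3.4 that each pregnancy and its linked infant contribute to one source only. Assign those that qualify in both the ORD and Market Clarity to one source by a fixed, pre-specified hierarchy, applied before matching.

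Do not exclude every ORD-sourced member from Market Clarity. Under Section 7.3.2 such a woman can fail the six-month claims enrolment rule and still meet the linked claims-EHR rule; a blanket exclusion would lose her from both sources in a study that is already short of exposed pregnancies. Assignment by hierarchy loses no distinct pregnancy.

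Report the overlap and the de-duplicated counts in the PSURs and the final report. Add a question on overlap with existing sources to the feasibility questionnaire (Section 7.7.2).

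The cost is one linkage step within one vendor's databases, and lower reported counts. The protocol does not say that Market Clarity records carry a marker of ORD origin, and Section 7.6 describes separate environments with de-identification limits, so the sponsor should confirm how shared members will be identified. If they cannot be, pool only sources that do not overlap, or report a sensitivity meta-analysis that leaves out one of the two.
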